REFERENCES	15

Confidentiality Statement

This document is confidential and is to be distributed for review only to investigators, potential investigators, consultants, study staff, and applicable independent ethics committees or institutional review boards. The contents of this document shall not be disclosed to others without written authorization from WCM.

List of Abbreviations

ACP	Advanced Care Planning
AE	Adverse Event
CFR	Code of Federal Regulations
CwC	Coping with Cancer
CRF	Case Report Form
CTSC	Clinical Translational Science Center
DSMC	Data Safety Monitoring Committee
DSMP	Data Safety Monitoring Plan
EoL	End of Life
FDA	Food and Drug Administration
GCP	Good Clinical Practice
GIST	Giving Information Strategically and Transparently
HIPAA	Health Insurance Portability and Accountability Act of 1996
HRBFA	Human Research Billing Analysis Form
HUD	Humanitarian Use Device
ICF	Informed Consent Form
IDE	Investigational Device Exemption
IND	Investigational New Drug
IRB	Institutional Review Board
PHI	Protected Health Information
PI	Principal Investigator
REDCap	Research Electronic Data Capture
SAE	Serious Adverse Event
SUSAR	Suspected Unexpected Serious Adverse Reaction
UIRTO	Unanticipated Problem Involving Risks to Subjects or Others
WCM	Weill Cornell Medicine

1. Protocol Summary

Full Title:	Giving Information Systematically and Transparently in Solid Tumor Cancer
Short Title:	Oncolo-GIST
Principal Investigator:	[name]
Study Description:	The study will develop, refine and pilot test the Oncolo-GIST clinician training intervention. The training is aimed at enhancing the clinician's communication with patients by teaching to relay information both sensitively and in simple terminology.
Sample Size:	Phase 1 Interviews: N=20 (N=10 clinicians, N=10 bereaved caregivers) Phase 2: N= 54 (N=50 patient subjects, N=4 clinician subjects)
Enrollment:	This study will enroll 74 subjects and screen up to 250 subjects.
Study Population:	Phase 1 Interviews: Bereaved Caregiver subjects will be caregivers of patients who died in the past year with a primary diagnoses of GI or lung cancers. Clinician subjects will be either oncologists, palliative care physicians, nurses, nurse practitioners, social workers and psychologists who care for patients with metastatic GI and lung cancers. Phase 2: Patient subjects will be adults (18+) diagnosed with lung, head and neck, or GI cancer, with a progression of their disease after one line of therapy. Clinician subjects will be Lung, Head and Neck, or GI oncologists. All subjects' primary language will be English and will have full mental capacity.
Enrollment Period:	Phase 1 (Interviews): 12 months Phase 2: 19 Months
Study Design:	Phase 1 (Interviews): Intervention manual development Phase 2: Intervention phase (two-group pilot randomized trial).
Participants:	Participants will be recruited at Weill Cornell Medical College/ New-York Presbyterian Hospital, at the Lung and GI Cancer centers.
Study Duration:	31 months Start date: Jan 22, 2020 End date: July 25, 2022 (end enrollment); January 25 th , 2023 (end data analysis and all other activities)
Participant Duration:	Phase 1 Interviews: 2 hours Phase 2: 4 months (with patient status monitoring up to 12 months)
Primary Objective:	To assess the effectiveness of the Oncologist intervention by examining the patient's degree of prognostic understanding after discussing

prognosis with either Oncolo-GIST trained or non-Oncolo-GIST trained clinicians.

Secondary Objectives:

To examine the effects on patients of having better prognostic understanding, including its effect on their quality of life, the type of care they choose to receive and whether or not the care they received was consistent with the patient's preferences and values.

Endpoints:

Outcome will be a training manual for clinicians that teaches the Oncolo-GIST methods of communication. The efficacy of the intervention will be determined by measuring the patient's prognostic understanding using our validated 4-item assessment. The assessment will determine if the patient understood the scan results as well as the expected outcomes of treatments offered. Outcomes will also include whether a DNR order was completed for the patient, the patients quality of life (McGill Quality of Life measure) , patient performance status (e.g., Eastern Cooperative Oncology Group, ECOG), as well as the type care received (e.g., anticancer, intensive, palliative care).

1.1 Study Objectives

1.1.1 Objectives

Objective 1: To develop and refine Oncolo-GIST, an intervention aimed at enhancing clinicians' communication with patients by teaching to relay information both sensitively and in simple terminology, by receiving feedback from clinicians as well from bereaved family members of cancer patients.

Objective 2: To determine feasibility and acceptability of Oncolo-GIST in a cluster trial in 50 patients with advanced cancer and 4 clinicians.

Objective 3: To test the preliminary efficacy of Oncologist on the 1) patients prognostic understanding 2) Other aspects of patient care including type of care, quality of life, and "value consistent" care.

1.1.2 Hypotheses / Research Questions

Hypothesis 1: The Oncolo-GIST intervention will be demonstrated to be feasible and acceptable to both clinicians and patients.

Hypothesis 2: The Oncolo-GIST intervention will be associated with advanced cancer patients' understanding of their scan results and prognosis (i.e., that they likely have months, not years, left to live).

2. Background and Significance

Informed consent requires an individual to have a clear understanding of the facts, implications, and consequences of an action.^{1 2 3} Bioethical principles, rooted in a respect for human dignity, necessitate that patients have a basic understanding of their illness and the risks and benefits of treatments proffered. Patients cannot make informed decisions about their care in the absence of knowledge of their prognosis or expected outcomes of treatments under consideration. It is alarming how unaware of their prognosis the vast majority of patients in our NCI-funded Coping with Cancer (CwC) R01s proved to be. Among CwC advanced cancer patients with a median survival of 5 months from our baseline assessment, we found only 5% accurately understood that they had incurable cancer, were terminally ill, were at a late- or end-stage of their illness, and likely had months, but not years, left to live.⁴ These findings highlight the ethical imperative of ensuring that patients have sufficient understanding of their prognosis, and expected risks/benefits of treatments being offered to them, for making informed choices. Preliminary evidence from CwC has shown that patients who get the gist that death is near are more likely to: a) engage in advance care planning (ACP)^{5 6} b) receive less burdensome, intensive, and unbeneficial EoL care (e.g., fewer ICU stays, inappropriate palliative chemotherapy),^{5 6 7 8} and c) more value-consistent EoL care.⁶ Although we found that 71% of these patients state that they would want their oncologist to tell them their prognosis, only 17.6% stated that their oncologist had discussed their prognosis (i.e., life-expectancy) with them.⁹ We find that patient prognostic understanding is improved by oncologist discussions of prognosis,^{4 10 7} but that the manner of communication matters for patients to "get the gist" that death is near.¹⁰

These results suggest a compelling need for interventions that: a) promote oncologist discussions of prognosis with their advanced cancer patients, b) prove feasible to implement in clinic, c) are acceptable to oncologists, and d) improve patients' prognostic understanding. We believe that the Oncolo-GIST approach has enormous potential to address each of these needs. By enabling more patients to make informed medical choices, the Oncolo-GIST approach is expected to uphold bioethical principles by promoting patients' capacity to engage in truly informed medical decision-making which, based on prior findings, is also expected to result in better EoL outcomes (e.g., less intensive, more palliative and more value-consistent EoL care).^{3 7 11}

3. Study Design and Methods

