In Phase 2, for the pilot cluster RCT study (Aim #3), we will recruit adult patients (n=50) with metastatic GI, head and neck, or lung cancers with scan results that reveal progression (worsened disease) on an initial systemic treatment; that is, patients whose life-expectancy can reliably be estimated to be months, not years.^{5 9} Medical oncologists (n=4) who care for these patients will also be consented for study participation and half (n=2) will be randomized to receive the brief "Oncolo-GIST communication" training. The Oncolo-GIST training will provide instruction in how to introduce the topic of prognosis, describe scan results as "worse," prognosis as "likely months, not years," and expected treatment outcomes (e.g., "not expected to be cured by treatment," and expected impact on quality of life – that is, whether the anticancer treatment is likely to make them feel overall better or worse). We expect 12-13 patients will be clustered within each of the 4 oncologists. Hierarchical Linear Modeling (HLM) techniques will be employed to address the non-independence of patient assessments within each cluster. Patients (n=25) will be seen by either an Oncolo-GIST trained oncologist or an oncologist not trained in the intervention; that is, usual care (n=25). Patients in both arms will have met the same eligibility criteria (i.e., have similar prognoses).

Thus, we will get initial feedback on the Oncolo-GIST intervention from relevant stakeholders and key informants, obtain information on the patient and oncologist experience with the intervention and evaluate its feasibility and acceptability. Finally, we will obtain preliminary effect size estimates

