3.2 Interviews, Focus Groups, Surveys, and/or Observations

A. Administration

▪ Timing and Frequency

Phase 1 Interviews: Clinicians and bereaved caregivers will complete a one-time, 2 hour phone study session or REDCap survey (including embedded intervention manual) link.

Phase 2: Patients will be assessed in the week prior to their scheduled scan, within 1 week of the clinic visit in which progressive scan results are discussed, and then after their next two scans, if they have them, to explore intervention effects on primary and secondary outcomes, respectively. Oncologists will be assessed in the week following that same clinic visit to obtain their impressions of the discussion of prognosis and the patient's prognostic understanding. All these assessments will take 20-30 minutes.

Trained oncologists will complete a brief (5-minute) post-training quiz, and all oncologists will complete a brief (5-minute) survey on Oncolo-GIST at the end of the

study. Additionally, patients will be monitored via EPIC for progression of disease up to 12 months.

- *Location*

Phase 1 interviews of caregivers and clinicians will take place at a location convenient to the participant over the phone or via REDCap. Assessments of patients and clinicians in the pilot stage will take place in-person in clinic, at a time convenient for the participant at a different appointment, or over the telephone. Patients in Phase 2 will also have the option of completing the surveys themselves via a secure web link if this is more convenient to them.

- *Person Identifiers*

Co-investigators may review EPIC to identify potential participants who meet eligibility. Contact information and appointment information will also be collected for either in-person or letter (postal and email) recruitment. Only data from potential participants will be stored on secure servers. Patient subjects will also have data collected via medical chart abstraction including diagnoses, medications, advanced directives, and types of care received (e.g. hospice). These data will be deleted upon completion of the study.

B. Study Instruments

- Phase 1 Interviews for both clinician and bereaved caregiver subjects will consist of a survey including demographics and oncology based communication questions specific to either the clinicians or caregivers. After each section of the Oncolo-GIST manual, participants will answer open-ended questions about the module they just reviewed.

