- Phase 2 patients will be screened with a mental status questionnaire and health literacy assessment. At the first visit they will answer an assessment battery including but not limited to questions about treatment and mental status prior to discussing their scan results. After the scan results, patients will answer questions to assess prognostic understanding and treatment preferences at 3 post-scan time points (1 week after initial scan, one week after second scan, one week after third scan from enrollment)). Trained co-investigators will also collect data via medical chart abstraction. Clinicians (Phase 2) will answer an initial demographic survey and surveys including prognosis questions, patient understanding, and patient medical status for each patient participant. Clinicians trained in Oncolo-GIST will also complete a short post-training quiz to assess their understanding of the Oncolo-GIST manual. All clinicians will complete a brief study completion questionnaire to assess the feasibility and acceptability of the Oncolo-GIST method.

- Referral information

Data collected/received from participants will be reviewed within 24-48 hours and research study staff will be responsible for addressing elevated psychological symptoms/suicidality identified on the assessments so that timely and appropriate psychiatric assessment and care can be provided. If a participant at acute risk of self-harm or harm to others cannot be reached by the study team within 3 hours (after at least two phone call attempts and an email requesting a call back), the participant's emergency contact(s) will be contacted.

4. Study Design

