6.1 Schedule of Assessments

Table 1. Schedule of trial events for Phase 1 Interviews (Bereaved Caregivers and Clinicians)

	Pre-study	Visit 1 (Interview)
Screening	X	
Informed Consent (see note)	X	
Review of Oncolo-GIST intervention		X
Demographics		X
Oncology Based Communication Questions		X
Semi-structured Interview		X

Table 2. Schedule of trial events for Phase 2

	Arm	Pre-Study	Pre-Scan	Post-Scan 1 (approx. 1 week)	Post-Scan 2	Post-Scan 3	Post-Scan 4 (up to 12 months)
Short Portable Mental Status Questionnaire ^s	P	X					
Health Literacy Assessment (REALM) ^s	P	X					
Informed Consent	B	X					
Oncolo-GIST Training (Clinicians)	C*	X					
Demographics	P		X				
4 Item Illness Understanding	P		X				
Treatment Intent	P		X				
Treatment Preferences	P		X				
CWC II Psychological questions	P		X				
NCCN Distress Thermometer	P		X				
The Human Connection Scale	P		X	X	X	X	
HADS	P		X	X	X	X	
McGill Quality of Life Questionnaire	P		X	X	X	X	
PSWQ-Ultra Brief	P		X				
PANAS	P		X				
Primary Appraisal Secondary Appraisal (PASA) items (Threat and Challenge subscales only)	P		X				
Post Scan Clinician Questionnaire	C			X			
Medical Chart Abstraction	C				X	X	X
Post Scan Patient Questionnaire	P			X	X	X	
Training Quiz	C*	X					
Post-Study Questionnaire	C						X

C = Clinicians, P = Patients, B = Both, ^s= Screening, * = Intervention Arm Only

Note: The Post-Scan 4 Chart Abstraction will occur when monitoring if progression of the disease is found after Post-Scan 3 or the patient is deceased; up to 12 months.

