8.1 Sample Size/Accrual Rate

Phase 1 Interview: Sample size will be 10 clinicians and 10 bereaved caregivers recruited over 6 months.

Phase 2: The pilot clustered RCT will enroll 4 medical oncologists (2 Oncolo-GIST Version 2.0 trained; 2 usual care) and 50 patients (25 will receive care from an Oncolo-GIST Version 2.0-trained oncologist, 25 will receive usual care) within an 18-month recruitment period. Based on past recruitment yields in the GI and lung cancer clinics at WCM (e.g., recruitment of 60 advanced GI cancer patients alone in 18 months), we are confident that we can recruit this number of eligible patients within an 18-month period. Given this is an oncologist communication intervention, we expect the patient drop-out rate to be low. Fifty participants will ensure fairly stable estimates of intervention effects and confidence intervals and indicate if there is a “signal” that the intervention is helpful for promoting prognostic understanding. Using our validated 4-point prognostic understanding score⁴ as a continuous outcome, if Cohen’s d is large (0.8), with 48 patients and 4 oncologists, the power will be $> 80\%$. If the effect size is medium (0.5), power will drop to 30%.

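### Hypothesis 1 claims acceptability to patients, but no patient measure of acceptability is designated; the only instrument given that purpose goes to four oncologists, two of them untrained

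*Combined protocol and SAP*

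**What the plan says.** Objective 2 (Section 1.1.1) is "To determine feasibility and acceptability of Oncolo-GIST in a cluster trial in 50 patients with advanced cancer and 4 clinicians". Hypothesis 1 (Section 1.1.2) goes further and names the audiences: "The Oncolo-GIST intervention will be demonstrated to be feasible and acceptable to both clinicians and patients". Section 3.1 adds an intention to "obtain information on the patient and oncologist experience with the intervention and evaluate its feasibility and acceptability". Elsewhere the goal is narrower: Section 2 and the opening of Section 3.1 speak of acceptability to oncologists and do not mention patients.

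On measurement, Section 3.2 B says: "All clinicians will complete a brief study completion questionnaire to assess the feasibility and acceptability of the Oncolo-GIST method". Section 3.2 A describes the same step: "all oncologists will complete a brief (5-minute) survey on Oncolo-GIST at the end of the" study. In Table 2 (Section 6.1) it is the "Post-Study Questionnaire", coded for clinicians in both arms rather than for the intervention arm alone. Section 8.1 gives the respondents: "4 medical oncologists (2 Oncolo-GIST Version 2.0 trained; 2 usual care").

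For patients, Section 3.2 B says "patients will answer questions to assess prognostic understanding and treatment preferences at 3 post-scan time points". Table 2 also schedules the Human Connection Scale, HADS and McGill questionnaire after the scan. Section 8.3.1 plans effect-size estimates, hierarchical models and regressions for Phase 2, and does not mention feasibility or acceptability.

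**The concern.** A hypothesis that names two audiences needs a measure from each. Here one audience has a designated instrument and the other has none. The training teaches oncologists to tell patients plainly that their time is likely to be short, so whether patients find that acceptable is a central question. Distress scales and the stopping rule in Section 11 address a different one.

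This goes beyond missing wording. An analysis can be specified late, but patient ratings that were never collected cannot be recovered, least of all in a population in which the plan expects nearly half to die within 4 months of baseline.

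On the clinician side, half the respondents to the designated questionnaire will not have been trained in the method they are rating. The documents describe no later training for them and no separate reporting by arm.

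**Working it through.** The plan gives no sample size, threshold or precision for Hypothesis 1, so there is no figure to reproduce. The check sets the passages side by side and then asks what the available respondents could support.

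**Step 1. What is assigned to acceptability or feasibility**

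| Source in the plan | Respondent | Assigned to Hypothesis 1? |
|---|---|---|
| Study completion questionnaire (3.2 B; Table 2) | 4 oncologists, 2 trained | Yes, the only one |
| Post Scan Clinician Questionnaire (3.2, Table 2) | Oncologist, per patient | No, but bears on delivery |
| Training quiz (Table 2) | 2 trained oncologists | No |
| Post Scan Patient Questionnaire (Table 2) | Patients, three post-scan points | No; items not shown |
| Human Connection Scale, HADS, McGill (Table 2) | Patients | No |
| Accrual target, 50 patients at 3 a month for about 18 months (4.4) | n/a | No, but a feasibility yardstick |
| Retention and withdrawals (7.3.6) | n/a | No, but feasibility data |

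Feasibility therefore has data and one numerical yardstick, none of it labelled as such. Patient acceptability has no designated source.

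**Step 2. Clinician ratings**

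If all n respondents approve, the exact (Clopper-Pearson) lower 95% limit is 0.025^(1/n).

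- Two trained oncologists, 2/2: 0.025^(1/2) = 0.158, interval 15.8% to 100%.
- All four, 4/4: 0.025^(1/4) = 0.398, interval 39.8% to 100%.

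Even unanimity among all four is compatible with true acceptability below 50%. With n = 2 the only possible results are 0%, 50% and 100%, so this part can only be descriptive.

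**Step 3. Patient ratings, if asked**

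Section 8.1 places 25 patients with trained oncologists. Take 20/25 (80%) as an illustration; the plan gives no expected rate. Treating patients as independent, the exact 95% interval is 59.3% to 93.2%.

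That is too narrow, because the 25 sit within two oncologists, 25/2 = 12.5 each. With intracluster correlation ρ, the design effect is 1 + (12.5 − 1)ρ and the effective sample size is 25 divided by it. The documents give no ρ, so 0.05 and 0.10 are assumptions. The interval uses the same beta quantiles with the effective n and 80% of it as the count.

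| ρ (assumed) | Design effect | Effective n | Approximate 95% interval at 80% |
|---|---|---|---|
| 0 | 1 | 25 | 59% to 93% |
| 0.05 | 1 + 11.5 × 0.05 = 1.575 | 25/1.575 = 15.9 | 53% to 95% |
| 0.10 | 1 + 11.5 × 0.10 = 2.15 | 25/2.15 = 11.6 | 47% to 97% |

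Fewer than 25 may contribute, since Section 3.1 accepts that some patients will not progress during follow-up. Even so, the patient estimate is well short of the near-total uncertainty left by two raters.

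**The case against.** The strongest reply is that the gap is inferred from silence about a form that has not been seen. Section 3.2 B does not say that the post-scan patient questions cover only understanding and preferences. The Post Scan Patient Questionnaire is scheduled three times, its items are not reproduced, and Section 3.1 states the intention to learn about patients' experience. This stands as a limit. A reader might infer that there will be no patient data on acceptability at all, and the documents do not support that. They show only that no patient measure is designated and that no analysis would use one.

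Second, clinician evidence is wider than the completion questionnaire. Section 3.2 has oncologists report their impressions of the prognosis discussion for each patient, which could give up to 25 trained-arm reports. This also stands, for delivery. It is why the 16% to 100% interval applies only to the end-of-study ratings.

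Third, a reader might infer that Hypothesis 1 as a whole cannot be tested. That goes too far for feasibility, given the accrual target, the retention reporting and the per-visit reports.

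Fourth, a reader might treat acceptability as the go/no-go criterion for the larger trial. No section says so: Section 3.1 links the next trial to positive results on the targeted outcomes, and Section 8.3.1 links it to effect-size estimates.

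Fifth, descriptive reporting is defensible in an early-stage pilot, and the absence of a threshold is by itself only missing detail. That is fair, but Hypothesis 1 promises a demonstration, and descriptive reporting still needs a patient measure.

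Finally, the arm of each oncologist is known, so untrained answers can be separated at analysis, and they may say something about anticipated acceptability. Separate reporting therefore answers that concern, and exclusion is not required.

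**Conclusion.** The point holds in a limited form. Hypothesis 1 claims acceptability to patients, but the plan designates no patient measure for it, its own statements of the acceptability goal in Sections 2 and 3.1 stop at oncologists, and Section 8.3.1 has no matching Phase 2 analysis. The one designated instrument has four respondents, of whom two are trained. Feasibility is under-specified, not unmeasurable. The planned analysis of prognostic understanding is unaffected.

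The size is the contrast in the working: two informed end-of-study raters against up to 25 trained-arm patients whose acceptability ratings are not planned for. The patient figures rest on an illustrative 80% approval, an assumed ρ of 0 to 0.10, and all 25 patients responding. The conclusion about the missing designation does not depend on them. If the Post Scan Patient Questionnaire already holds a suitable item, the problem reduces to naming it and planning its analysis.

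**What to change.** 1. Add two or three items to the Post Scan Patient Questionnaire at Post-Scan 1, or designate existing ones: whether prognosis was discussed, whether it was clear, and whether the discussion was acceptable.
2. In Section 8.3.1, define patient acceptability as the trained-arm proportion rating the discussion acceptable. Report it with a confidence interval that allows for clustering within the two trained oncologists. Two clusters cannot estimate ρ usefully, so show the proportion for each oncologist and the interval over a stated range of ρ.
3. Report delivery from the existing Post Scan Clinician Questionnaire, and name accrual and retention as the feasibility measures.
4. Report the trained oncologists' acceptability ratings separately from the untrained ones, descriptively (n = 2).
5. If no patient measure is added or designated, remove patients and the claim of demonstration from Hypothesis 1, so that it matches the oncologist-only goal at the start of Section 3.1, and reconcile the later sentence there about patient experience.

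Any numerical success threshold is the sponsor's choice; the documents offer no basis for one. The cost is about one minute per patient in an interview already scheduled, plus short text changes in Sections 1.1.2 and 8.3.1.
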